Obstructive Sleep Apnea Syndrome (OSAS) is a very common disorder with a high prevalence in the general population. Common manifestations of OSAS include snoring, excessive daytime sleepiness, fatigue as well as long term sequelae like memory loss and attention deficits¹, hypertension, arrhythmias, coronary artery disease², congestive heart failure, stroke³ and insulin resistance⁴. Given the significant impact of OSAS on overall health and quality of life, it is very important to treat it optimally. The treatment of OSAS most commonly involves the use of Continuous Positive Airway Pressure (CPAP) to maintain patency of the upper airway. Nonadherence rates to CPAP are variable and range from 29% to 83%⁵⁻⁷ in various studies. One of the common reasons for non-compliance with CPAP usage is mouth dryness⁸. Mouth dryness or xerostomia also impairs sleep quality and overall quality of life⁹ and can be further exacerbated in patients who are mouth-breathers or have underlying conditions predisposing to xerostomia. Anecdotally, in our clinical experience, approximately 80%-90% patients with OSAS on CPAP therapy complain of dry mouth. In about 1/3rd of these patients, the sensation of mouth dryness is significant and bothersome enough to decrease compliance with CPAP. The addition of heated humidification may improve the mouth dryness but has a variable impact on CPAP compliance with some recent studies showing no improvement in CPAP compliance at all⁹. Given the significant adverse effects of OSAS on health, alternative measures to improve CPAP compliance in patients with OSAS need to be considered and evaluated. . As part of this initiative, our study aims to show improvement in patient CPAP compliance with the use of NeutraSal, a supersaturated calcium phosphate rinse, targeted at treating the dry mouth associated with CPAP therapy.

Study Trial (Post-market)

NeutraSal in the Management of Xerostomia in Obstructive Sleep Apnea Syndrome patients utilizing CPAP therapy

Study Population:

Patients are male or female, ages 18-84, with a diagnosis of obstructive sleep apnea syndrome (OSAS), who have been started on CPAP treatment and have subsequently complained of dry mouth or developed worsening of a pre-existing dry mouth condition, as an effect of CPAP treatment.

Study Design:

Randomized, double- blinded, study of OSAS patients undergoing CPAP therapy designed to observe the impact of NeutraSal on compliance to CPAP therapy as compared to placebo.

Sample Size

~32 patients per site (16 in study group and 16 in placebo group)

Population

The population will be composed of patients with a confirmed diagnosis of OSAS who are on CPAP therapy, have developed new onset of dry mouth or have worsening of pre-existing dry mouth condition, as an effect of CPAP treatment, meet the other inclusion criteria and do not have any exclusion criteria.

Trial Duration

Ongoing recruitment; subjects will be followed for 12 weeks from the time of enrollment in the study.

Trial Agent and Intervention Description (If applicable)

NeutraSal, dosed 2 times per day at waking and bedtime (indications 2-10 times per day or PRN), swish and spit, daily for a term of 12 weeks.

Primary Objective

To observe the impact of NeutraSal on OSAS patients compliance to CPAP therapy compared to placebo.

Secondary Objective

To assess whether the daily use of NeutraSal will prevent or reduce dry mouth perception in patients undergoing CPAP therapy

Tertiary Objective

To assess whether NeutraSal will balance the pH of the oral mucosa long term (3 months)

Efficacy Measurements:

1. Compliance with use of cpap
2. Xerostomia Questionnaire
3. Resting Saliva pH Testing
4. Product Utilization based on Patient Diary

Exit Evaluation:

1. Brief Physical Exam for Overall Health
2. Final collection of patient information during visit on data form
3. Final review of efficacy measurements

Study Population:**Inclusion /Exclusion Criteria**

The inclusion criteria will be as follows:

1. Patient should be above 18 years of age.
2. Patients who have been initiated on CPAP therapy after an initial diagnosis of OSAS and have developed dry mouth or have worsening of pre-existing dry mouth condition, as an effect of CPAP therapy.
3. Ability to attend visits at the research site
4. Patient should be able to read and/or understand and sign the consent form be willing to participate in the research study

The exclusion criteria are as follows:

1. Patients with open mouth sores at study entry.
2. Any pathology that, based on the judgement of the researcher, could negatively affect the oral mucosa and subsequent treatment for xerostomia (immune disorders, etc.)
3. Patients using any other prophylactic mouthwashes.
4. Patients who are pregnant and/or nursing.
5. Patients becoming pregnant during the treatment period will be removed from data.
6. Patients on a low sodium diet
7. Patients currently on medication or treatment for xerostomia
8. Patients < 18 years of age
9. Hypersensitivity to any of the following ingredients- sodium chloride, sodium phosphate, calcium chloride and sodium bicarbonate

Trial drug /Interventions:

NeutraSal is a powder that when dissolved in water creates a supersaturated calcium phosphate rinse.

Placebo is a powder consisting of sodium chloride only. Sodium chloride has been chosen as a placebo because it looks like Neutrasal and can be packaged (in foil) like Neutrasal for a double blind effect.

For the study, NeutraSal or placebo will be dispensed by the investigator for the treatment length in a randomized, double-blind procedure. Patients will be provided pre-measured cups, timer to measure length of time patient gargles and patient instructions. Patients will mix product(s) at home in a clean glass or supplied pre-measured cup.

Trial Schedule:

Projected Start Date: July 1st, 2013

Patients with OSAS seen in MUSC (Medical University of South Carolina) sleep clinic who are on CPAP, meet the inclusion criteria and do not have any exclusion criteria, will be invited to participate. After obtaining informed consent, patients will be randomized to the study or placebo groups. The study sponsor, Invado pharmaceuticals will provide a randomization schedule and key. The packets of product and placebo will be numbered 1-32 based on the randomization. Patient 1 will get bag 1, patient 2 will get bag 2 and so on. The study product NeutraSal and placebo will be packed in identical bags. Both the investigators and patients will be blinded to the contents of the bags, hence this will be a double-blind study. Patients will begin taking NeutraSal or placebo at the start of therapy and continue through 12 weeks of treatment.

Patients will receive a baseline visual examination of the oral mucosa in addition to a brief physical exam by the investigators and study coordinator at visit one and receive samples of the product. Patients will be given a diary or questionnaire to record compliance to the product and Xerostomia symptom relief. Patients will be monitored by the principal investigator and the study coordinator via office visit on the baseline visit, visit at 6 weeks and a final visit at 12 weeks.

During these visits the principal investigator and study coordinator will measure the following:

- Xerostomia Questionnaire
- CPAP Compliance measured by objective CPAP downloads as outlined in the follow up visits section
- Product Utilization and Compliance to Dosing (Patient Diary Reviewed)
- Adverse Effects
- Resting salivary pH

Schedule of Study Events:

	Baseline Visit	6 Weeks	12 Weeks
Medical History	X		
Brief Physical Exam	X	X	X
Pregnancy Test	X	X	X
Informed Consent Form	X		
Inclusion/Exclusion Criteria	X		
Treatment Administration	X	X	X
Xerostomia Questionnaire	X	X	X
Resting pH	X	X	X
Compliance Report/ Patient Diary	X	X	X
Adverse Effect Monitoring	X	X	X

Data collection instruments are included in the IRB submission.

Screening Visit/ Initial Visit

During this visit, OSAS patients on CPAP who are eligible for study enrollment will be given information about the study. An informed consent form will be reviewed and signed. Subjects will receive a brief physical medical exam and a baseline visual examination of the oral mucosa. Once enrolled in the research study, patients will receive either medication or placebo in a randomized selection. Patients will also complete an oral questionnaire on the state of xerostomia. Researchers will do a baseline pH test of the oral mucosa. Patients will be

instructed on proper use of neurasal or placebo. Patients will be given a diary or questionnaire to record compliance to the product and Xerostomia symptom relief.

Follow Up Visits

Patients will complete an oral questionnaire on the state of xerostomia since the initial visit and compliance with CPAP therapy will be reviewed by history and by objective CPAP compliance downloads. Researchers will also review the patient diary for compliance to dosing for medication. CPAP compliance will be recorded as the number of days that the patient used CPAP for ≥ 4 hours/day and the average number of hours of nightly usage. CPAP compliance downloads are provided by durable medical company (DME) providers and usually indicate both of these measures. The dates between which the compliance is measured are also indicated on the compliance downloads provided by the DME providers. CPAP compliance will be recorded on the 2nd visit at 6 weeks and the 3rd visit at 12 weeks. Every effort will be made to obtain CPAP compliance from the date that subjects are started on neurasal/placebo until the dates of the study visits. If CPAP compliance for the entire period of 6 weeks before the 2nd visit and 3 months before the 3rd visit is not available, then any compliance data from a point after subjects received the study drug till a date in the 5-7 week period around visit 2 and in the 10-12 week period around visit 3 will be recorded. The date range of the available compliance data will also be recorded.

If any patients miss follow-up visits, then phone follow-up will be done to obtain information about their product utilization, compliance to dosing and xerostomia symptom relief. CPAP compliance downloads for these patients will be obtained from the DME providers.

Adverse Event Reporting:

Adverse Event (AEs) and Serious Adverse Event (SAEs) will be reported immediately, if suspected to be related to treatment.

Subject Withdrawals:

Subjects will be advised that they are free to withdraw from the study at any time for any reason, or, if necessary, the Investigators may withdraw a subject from the study, according to the following criteria, to protect the subject's health:

- Intolerable adverse effects
- Major violation of study protocol procedures
- Non-compliance with protocol
- Subject unwilling to proceed or consent is withdrawn
- Pregnancy

Statistical Analysis Plan:

This is a double-blind, randomized, intention to treat, controlled clinical trial comparing Neurasal to Sodium Chloride placebo in a 1:1 randomization. The primary analysis is a comparison of CPAP compliance measured by days CPAP was used for ≥ 4 hours per night over 12 weeks.

The secondary analyses include:

1)CPAP compliance as measured by average number of hours of daily CPAP use.

- 2) improvement in the total score of the Xerostomia questionnaire measured at baseline and 12 weeks.
- 3) Change in resting salivary pH between baseline and 12 weeks.

Statistical analysis will be performed using two sided t-test with $p < 0.1$ being considered significant for this pilot study. Missing data will be treated by use of last data carried forward methodology.

Sample size determination

This is a pilot study in which there are no previous data to determine an accurate sample size that would definitively prove or exclude the possibility of a treatment effect. We estimate the treatment to be effective at improving CPAP compliance in 25% of subjects. This would translate to the same estimated increase in number of days in which CPAP is used for ≥ 4 hours. Therefore, a sample size of 30 subjects is needed to obtain an 80% confidence level with a response rate of 25%. We estimate that 2 subjects will drop out, therefore we will need 32 subjects for this study.

Informed Consent Process:

The language and writing of an informed consent will be at a 6th grade level. No potentially vulnerable subjects will be enrolled in the study, such as, pregnant and lactating women, children, prisoners, cognitively impaired and critically ill subjects.

Privacy and confidentiality:

Human subjects' names will be kept on a password protected database, and will be linked only with a study identification number for this research. There will be no patient identifiers. All data will be entered into a computer and kept on password protected network storage. Hard copies of the records collected as a part of this study will be kept in a locked office. Only the study personnel will have access to the study records.

Risk/Benefit:

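### Exclusion 5 deletes randomised subjects who become pregnant, which contradicts the plan's unqualified intention-to-treat statement (wrong as written; low expected impact)

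*Combined protocol and SAP*

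**What the plan says.** Four places in the combined protocol and SAP bear on the main point.

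- **Inclusion/Exclusion Criteria, exclusion 5:** "Patients becoming pregnant during the treatment period will be removed from data".
- **Statistical Analysis Plan:** "This is a double-blind, randomized, intention to treat, controlled clinical trial". No exception is given and no modified analysis set is defined.
- **Subject Withdrawals:** "the Investigators may withdraw a subject from the study, according to the following criteria". Pregnancy is the last criterion listed. The list does not say that data already collected are deleted.
- **Schedule of Study Events:** the row "Pregnancy Test" is marked at baseline, 6 weeks and 12 weeks. Trial Schedule places randomisation directly after consent.

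For the subordinate point, the primary endpoint is CPAP compliance "measured by days CPAP was used for ≥ 4 hours per night over 12 weeks". The Statistical Analysis Plan handles missing data by carrying the last data forward, without saying whether a count or a rate is carried. Follow Up Visits aims for a download covering the whole period. As a fallback it accepts one that starts at any point after product was received and ends within weeks 5-7 (visit 2) or weeks 10-12 (visit 3). It records the date range, and it obtains provider downloads for patients who miss visits.

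**The concern.** A subject can become pregnant during treatment only after being randomised. Although it sits in an eligibility list, exclusion 5 is therefore a rule about the analysis set: it removes randomised subjects because of a later event. Intention to treat is meant to prevent exactly that. Two analysts could follow the same document, analyse different sets of subjects, and each cite a sentence in support. The choice could even be made after results are known.

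The deletion need not coincide with missing data. With a test at week 12, a subject could complete the study, supply a full 12-week download and still be dropped at the final visit.

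The subordinate point concerns how incomplete follow-up enters the primary endpoint. If a raw count from a shorter period stands in for a 12-week count, it is too low whenever CPAP use continued. This reaches beyond pregnancy, since the plan expects two dropouts.

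**Working it through.** **Text comparison (decides the main point).** Exclusion 5 acts after randomisation and removes data. The Statistical Analysis Plan declares intention to treat without qualification. Subject Withdrawals already covers pregnancy and does not mention deletion. The carry-forward rule makes no exception for pregnancy. No section reconciles these statements, so the contradiction needs no calculation.

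**Inputs from the documents.** Allocation is "16 in study group and 16 in placebo group"; the plan's total is 30 + 2 expected dropouts = 32. Twelve weeks is 84 days and six weeks is 42 days. The test is two-sided at 0.10. The plan gives no SD, no expected pregnancies and no figure for the effect of removal.

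**Assumptions.** SD of the day count 20 to 30; the deleted subject lies d = 20 to 42 days from the mean of the other 15; a difference of 21 days (25% of 84) for the power illustration; CPAP used for at least 4 hours on 80% of nights.

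**Size of one deletion.**

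- Share of the arm: 1/16 = 6.25%; of the trial: 1/32 = 3.1%.
- If the other 15 have mean m, the full-arm mean is (15m + m + d)/16 = m + d/16. Deletion moves the arm mean by d/16: 20/16 = 1.25 and 42/16 = 2.625 days.
- Standard error of the difference = SD × √(2/16): 7.07 days at SD 20 and 10.61 at SD 30.
- Ratios: 1.25/10.61 = 0.12 to 2.625/7.07 = 0.37.
- Power by normal approximation, Φ(21/SE − 1.645), 16 v 16 against 16 v 15: 0.907 to 0.899 (SD 20), 0.768 to 0.756 (SD 25), 0.631 to 0.619 (SD 30). The loss is about one percentage point.

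**Subordinate point: raw count from a window of w days, use unchanged at 80%.** Shortfall against the 84-day count = (84 − w) × 0.8.

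| Window | Shortfall per subject | Arm mean (÷16) |
|---|---|---|
| 42 days | 42 × 0.8 = 33.6 days | 2.1 days |
| 14 days (e.g. weeks 8 to 10) | 70 × 0.8 = 56 days | 3.5 days |

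If use stopped for good at the end of a window that began at the start of treatment, the shortfall is zero.

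**Error of the alternative (scaling the rate to 84 days), observed rate 80%.** If there was no use on the unobserved days, scaling overstates the count by the same amounts: 33.6 days (2.1 on the arm mean) for 42 days and 56 days (3.5) for 14 days. If every unobserved night was compliant, it understates by (84 − w) × 0.2: 8.4 days (0.525) and 14 days (0.875).

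**The case against.** The strongest reply is that exclusion 5 is loose wording for withdrawal and will seldom, if ever, be used. Pregnancy at entry is excluded, and for the rest the protocol says "Patients are male or female, ages 18-84". The rule is written in advance, triggered by a test and applied under blinding, and nothing suggests that pregnancy depends on the arm. One removal costs about one point of power.

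Most of this stands as to size. It does not remove the contradiction: withdrawal for pregnancy is already covered under Subject Withdrawals, so exclusion 5, read literally, adds the deletion of data. If only withdrawal was meant, striking the sentence loses nothing.

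A second reply points to Informed Consent Process: "No potentially vulnerable subjects will be enrolled in the study", with pregnant women among those named. That sentence governs enrolment. It does not call for discarding data from someone eligible when enrolled.

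On the subordinate point, the sponsor can say that the plan may intend a rate, and that the recorded date ranges and provider downloads already supply what a rate needs. That is fair, and is why the point is conditional. The download provision does not, however, expressly name withdrawn subjects.

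**Conclusion.** The contradiction between exclusion 5 and the intention-to-treat statement is certain from the text. Its expected numerical effect is low. The 1.3 to 2.6 days (0.12 to 0.37 standard errors) is the shift in one realised arm mean if one such subject is deleted, under the assumed distances and SDs. It is not an expected bias.

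Three stronger readings are tempting, and the documents do not support them.

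- A reader might infer that the rule biases the comparison towards one arm. No number of pregnancies, and no reason for a difference by arm, is given.
- A reader might infer that the primary analysis will carry a raw 6-week count forward as a 12-week count. The plan does not say which quantity is carried.
- A reader might take a download ending at week 10 to be at most 14 days short, and so a minor matter. The fallback lets the start vary too, so a window of only 14 days can qualify.

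The subordinate point therefore stands only if a raw count is used and CPAP use continued. At an assumed 80% use its size per subject is then 2.1 days on the arm mean for a 42-day window and 3.5 days for a 14-day window.

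**What to change.** **Main change.** Delete the sentence in exclusion 5. State in the SAP that all randomised subjects, including those who become pregnant, are analysed in the arm to which they were randomised. Use provider downloads where consent and the IRB allow; otherwise use the data collected up to that date. Make explicit that the missed-visit download provision also covers withdrawn subjects on the same terms. Withdrawal and product-stopping criteria are unchanged.

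**Subordinate change.**

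- Define the primary endpoint as days with at least 4 hours of use, divided by days in the recorded date range, times 84. Do not use a raw partial count.
- Report by arm the number of scaled subjects and their window lengths.
- Add a sensitivity analysis that counts unobserved days as non-use.
- For subjects with no on-treatment download, name one primary value before unblinding and report 0 and 84 days as sensitivity extremes. These differ by 84/16 = 5.25 days of arm mean per subject, so the primary choice must not be left open.

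**Cost.** Wording changes in the protocol, SAP and, where needed, consent form, and a few extra download requests. There are no extra visits; the sample size stays at 32 and alpha at 0.10. The downside is that scaling assumes use on unobserved days matches observed days. It can err in either direction, and by more for short windows: up to 3.5 days on the arm mean per subject for a 14-day window at 80% use.

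### Pre-treatment CPAP use is not clearly recorded, and the unadjusted t-tests, though valid, may waste precision at about 15 per arm; baseline adjustment would be a cheap gain

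*Combined protocol and SAP*

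**What the plan says.** **Who is enrolled.** Study Population describes patients "who have been started on CPAP treatment and have subsequently complained of dry mouth". CPAP use before the study product should therefore exist for most of them. The inclusion and exclusion criteria set no upper or lower limit on it.

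**When CPAP use is recorded.** The sections differ:

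- Follow Up Visits: "CPAP compliance will be recorded on the 2nd visit at 6 weeks and the 3rd visit at 12 weeks". The intended window starts with the product ("Every effort will be made to obtain CPAP compliance from the date that subjects are started on neurasal/placebo"), and so does the fallback ("any compliance data from a point after subjects received the study drug").
- Trial Schedule: names baseline, 6 and 12 weeks as the visits, then lists among the measures "CPAP Compliance measured by objective CPAP downloads as outlined in the follow up visits section". That includes baseline on its face but defers to the section above, which does not.
- Screening Visit/ Initial Visit: names a xerostomia questionnaire and a pH test ("Researchers will do a baseline pH test of the oral mucosa"), but no CPAP download.
- Schedule of Study Events: the row "Compliance Report/ Patient Diary" is ticked at all three visits without saying whether it means CPAP or product compliance. The same section adds "Data collection instruments are included in the IRB submission"; those forms are not in the documents.

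**How it is analysed.** The Statistical Analysis Plan compares days with at least 4 hours of use over 12 weeks (primary) and mean daily hours (first secondary) as on-treatment values. Xerostomia score and salivary pH are taken as change from baseline to 12 weeks. All use a two-sided t-test at 0.10. No covariate is named, and the only missing-data rule is to carry the last value forward.

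**The concern.** How much a patient used CPAP before randomisation may well predict use over the next 12 weeks. If it is not collected, or is collected and not used, differences between patients that pre-date treatment stay in the error term. In a trial sized at 30 evaluable subjects, that can widen the interval for the primary comparison without need.

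The recording gap also matters on its own. Staff could read the sections differently and obtain a baseline download for some patients only. A pilot that lacks baseline use cannot report the correlation between prior and later use, which would help to size a later trial.

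For xerostomia and pH the baselines are collected, but the change score fixes the baseline coefficient at 1. That is valid, and usually less efficient than estimating the coefficient.

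**Working it through.** **The plan's own figure.** Sample size determination gives 30 evaluable plus 2 dropouts: 30 + 2 = 32. The 30 cannot be rebuilt from the stated inputs, because no control rate, SD or power is given. Nothing below depends on it beyond n = 15 per arm.

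**Inputs from the documents.** 1:1 allocation, 30 evaluable (15 per arm), two-sided alpha 0.10.

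**Assumptions.** Power 80%. Correlation r between pre-treatment and on-treatment use from 0 to 0.7. Fraction f of baselines missing and replaced by the pooled mean: 0, 20% or 50%. The documents give none of these.

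**Unadjusted t-test.** SE = √(2/15) = 0.365 SD. By the noncentral t on 28 df, 80% power needs a noncentrality of about 2.55, so the detectable difference is 2.55 × 0.365 = 0.931 SD. The 90% CI half-width is 1.701 × 0.365 = 0.621 SD.

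**ANCOVA.** 27 df; the variance is multiplied by (1 − r²(1 − f)) × (1 + 1/26). At r = 0.5 and f = 0 this is 0.75 × 1.038 = 0.779, with square root 0.882. The detectable difference is 0.931 × 0.882 ≈ 0.822 SD and the half-width 1.703 × 0.882 × 0.365 ≈ 0.549 SD. Across the range:

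| r | Detectable, f = 0 | f = 20% | f = 50% |
|---|---|---|---|
| 0 | 0.949 | 0.949 | 0.949 |
| 0.2 | 0.930 | 0.934 | 0.940 |
| 0.3 | 0.906 | 0.915 | 0.928 |
| 0.5 | 0.822 | 0.849 | 0.888 |
| 0.7 | 0.678 | 0.740 | 0.825 |

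Adjustment breaks even with 0.931 SD at r of about 0.20, 0.22 and 0.28 for f = 0, 20% and 50%.

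**In patients.** An unadjusted trial of equal sensitivity would need, for f = 0 / 20% / 50%, 15.8 / 15.5 / 15.1 per arm at r = 0.3 and 19.0 / 17.9 / 16.4 at r = 0.5.

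**In power.** At a true difference of 0.931 SD with complete baselines, power is 78.6%, 81.9%, 87.9% and 96.1% at r = 0, 0.3, 0.5 and 0.7, against 80% unadjusted.

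**Validity.** In 100,000 simulated normal trials at each of r = 0, 0.5 and 0.7, type I error at nominal 0.10 was 0.098–0.100 for both tests. A second simulation (40,000 trials) kept the outcome as days out of 84, with percent of nights over 7–28 pre-treatment nights as covariate. Type I error was 0.098–0.103 for ANCOVA and 0.096–0.104 for the t-test. At r of about 0.53 and an assumed SD of 23.7 days, the mean 90% half-width was 12.6 days (13.1 with 20% imputed) against 14.7 unadjusted.

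**Xerostomia and pH.** With equal variance before and after (assumed), a change score has variance factor 2(1 − r). It detects 0.931 × √(2(1 − r)) = 1.101, 0.931 and 0.721 SD at r = 0.3, 0.5 and 0.7, against 0.906, 0.822 and 0.678 SD with ANCOVA.

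**The case against.** - **No error is shown.** A prespecified t-test in a self-described pilot is valid, and so is a change score. This stands, and it limits the point to a recommended improvement.
- **The benefit depends on an unknown r.** This also stands. Some patients may be recent CPAP starters whose early use predicts later use poorly. Below r of about 0.2 adjustment loses slightly, and at 0.3 it is worth less than one patient per arm. The worst case is still small: 0.949 − 0.931 = 0.018 SD lost at r = 0, against 0.931 − 0.822 = 0.109 SD gained at r = 0.5.
- **A baseline download may already be planned.** No product use can have been logged before the product is dispensed, so the baseline tick could mean a CPAP report; it could equally mark handing out the diary. The IRB forms may settle this. The protocol text does not, and the missing covariate remains either way.
- **Variable windows weaken the link.** On-treatment downloads may start late and end in weeks 10–12, and a carried-forward 6-week count could stand in for 12 weeks. In one check with assumed beta-distributed use, r fell from 0.55 with full windows to 0.50 when 25% of subjects had windows of 28–84 nights and to 0.47 when 50% did; the detectable difference went from 0.79 to 0.82 and 0.84 SD. The gain shrinks but stays within the range tabulated.
- **Pre-treatment data may be hard to get.** The protocol is cautious even about on-treatment downloads. The columns for 20% and 50% imputed show what that would cost.

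**Conclusion.** The concern holds, as a point of clarity and efficiency. The sections conflict on whether pre-treatment CPAP use is recorded, and the SAP makes no use of it for the primary endpoint or mean hours. The planned tests remain valid.

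With complete baselines, adjustment ranges from a loss of about 0.02 SD in detectable difference (r = 0) to a gain of about 0.11 SD at r = 0.5 and 0.25 SD at r = 0.7. These sizes rest on 15 evaluable per arm, 80% power, approximately normal outcomes and an assumed r. For xerostomia and pH, ANCOVA detects a smaller difference than the change score at each r shown, given equal variances. The small downside and low cost make the change worth making.

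**What to change.** 1. **Recording.** In the Screening Visit and Follow Up Visits text, state that a dated pre-treatment CPAP download (for example, up to 4 weeks before product start, using the nights available) is obtained with the existing provider request, in the same way for both arms. The 4 weeks is only an example. Split the combined schedule row into one for the CPAP download and one for the patient diary, and align the Trial Schedule list.
2. **CPAP endpoints.** In the SAP, compare days with at least 4 hours of use, and mean hours, each by ANCOVA with treatment and the matching pre-treatment measure (percent of nights with at least 4 hours, or mean hours). Keep two-sided alpha at 0.10, report the adjusted difference with its 90% CI, and keep the unadjusted t-test as a sensitivity analysis. The primary outcome can stay as days; moving to percent of available nights is a separate choice, tied to the variable windows.
3. **Missing baselines.** Replace a missing pre-treatment measure by the mean of observed values in both arms combined. Carry-forward cannot fill a baseline, so this rule is needed.
4. **Xerostomia and pH.** Compare the 12-week value by ANCOVA with treatment and its own baseline.

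**Cost.** For CPAP, one earlier date range on downloads already requested, plus SAP wording; for xerostomia and pH, wording only. The price is one degree of freedom, a slight loss if r is below about 0.2, and a smaller gain where pre-treatment records are short or missing.

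### The primary outcome is a raw count of CPAP days over 12 weeks, but the download rules do not hold the counted period to 84 nights

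*Combined protocol and SAP*

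**What the plan says.** The period for the primary outcome is described in several ways.

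- **Statistical Analysis Plan:** the primary analysis is a "comparison of CPAP compliance measured by days CPAP was used for ≥ 4 hours per night over 12 weeks". No denominator is given.
- **Follow Up Visits, main rule:** staff try to obtain data "from the date that subjects are started on neurasal/placebo until the dates of the study visits".
- **Follow Up Visits, completeness test:** the fallback applies if compliance for the "entire period of 6 weeks before the 2nd visit and 3 months before the 3rd visit is not available".
- **Follow Up Visits, fallback:** staff may then use a download that starts at any time once the subject has the product and runs "till a date in the 5-7 week period around visit 2 and in the 10-12 week period around visit 3".
- **Follow Up Visits, missed visits:** downloads come from the equipment provider, and no date range is stated.
- **Trial Agent and Intervention Description:** the product is used as "swish and spit, daily for a term of 12 weeks".
- **Trial Duration:** "subjects will be followed for 12 weeks from the time of enrollment in the study". The Trial Schedule puts the last visit at 12 weeks and gives no tolerance in days.

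The date range of each download is recorded, but nothing in the Statistical Analysis Plan uses it. The missing-data rule carries the last value forward and does not say how to treat a report that covers only part of the period.

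**The concern.** A raw count is bounded by the number of nights it is drawn from. If that number differs between subjects, part of the variation in the outcome reflects scheduling and report format rather than CPAP use. Under the main rule, a late visit 3 brings in nights beyond the 12-week product term. An early visit, or a fallback report, removes nights. Two subjects with identical habits can then have clearly different values of the primary outcome.

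With 32 subjects and a t-test on the counts, this extra variation costs precision. If visit or report timing differs between arms, it also shifts the estimated difference.

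**Working it through.** The plan states no figure for the length of the window, so there is none to reproduce. The check is calendar arithmetic on each rule.

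**1. Endpoint period.** 12 weeks × 7 = 84 nights.

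**2. Completeness test.** Three calendar months span 89 to 92 days depending on the start date. The excess over 84 is 5 to 8 nights, or 5/84 = 6.0% to 8/84 = 9.5%. Taken literally, a full 84-night record at a week-12 visit fails this test.

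**3. Start and end of each rule.**

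| Rule | Start | End | Nights |
|---|---|---|---|
| Statistical Analysis Plan | not stated | not stated | 84 |
| Main rule | product start | actual visit 3 | 84 only if the visit is on time |
| Fallback | any point after study drug received | weeks 10 to 12 | at most 70 to 84, no minimum |
| Missed visit | not stated | not stated | undefined |

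The fallback stops by week 12. The main rule does not.

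**4. Late visit under the main rule.** Extra counted days = days late × share of nights with at least 4 hours of use. The documents give neither input. Assume 7 or 14 days late and a share of 40% to 70%:
- 7 days late: 7 × 0.40 = 2.8 to 7 × 0.70 = 4.9 extra days (ceiling 7)
- 14 days late: 14 × 0.40 = 5.6 to 14 × 0.70 = 9.8 extra days (ceiling 14)

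**5. Short windows.**
- Visit one week early (assumption): 84 − 7 = 77 nights at most
- Fallback ending at week 10: 10 × 7 = 70 nights at most, and (84 − 70)/84 = 16.7% fewer. At a 40% to 70% share, the expected count is 28.0 to 49.0 rather than 33.6 to 58.8.
- Fallback from week 6 to week 10 (assumed start): 28 nights, for an expected count of 11.2 to 19.6

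**6. Scale against the planned effect.** Sample size determination expects a 25% effect and carries the same figure over to the number of days. If that is read as a relative increase (assumption), and the share of nights with sufficient use is the same in the extra week, an average timing difference of one week between arms moves the count by 7/84 = 8.3%. That is 8.3/25, about one third of the planned effect.

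**The case against.** The strongest reply is that the plan already limits the period. The analysis, the follow-up and visit 3 are all set at 12 weeks, the fallback cannot run past week 12, and recorded date ranges would reveal an overlong report. Blinding and identical packaging also make a timing difference between arms less likely. Much of this is fair, and it keeps the point small. It does not settle the matter: the main rule ends at the actual visit, no tolerance is given for that visit, and no analysis rule applies the recorded dates.

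Two stronger readings are tempting, and the documents do not support them.

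- *A reader might infer that nights before product start are counted, because three months back from a week-12 visit reaches 5 to 8 nights before it.* Both collection rules start at or after the start of product. The three-month phrase is only the condition that triggers the fallback, and the Tertiary Objective uses three months loosely for the same follow-up.
- *A reader might infer that nights after the product term dilute the difference between arms.* In a raw count, if those nights carry no treatment effect and occur equally in both arms, they add the same expected number of days to each. The mean difference is unchanged and only noise is added. Dilution would apply to a per-night measure, such as the secondary outcome of average hours.

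**Conclusion.** The concern stands as a conflict between the stated endpoint and the stated collection rules. The endpoint is a count over 84 nights, while the rules allow a longer window when visit 3 is late, a shorter one when it is early, and a window of no fixed start or length under the fallback. The size is up to 7 days, or 8.3% of 84, per week of lateness. The maximum is 77 nights for a visit one week early and 70 for a fallback ending at week 10. The consequence is added noise, with bias only if timing differs between arms.

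The documents do not say how many subjects would be affected or how late visits run, so the total effect on the trial cannot be computed. It could be nil if every visit is on time and every report is complete. This is a minor point that is cheap to correct.

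**What to change.** Reconcile the passages to one counting window, nights 1 to 84 from first product use, in both Follow Up Visits and the Statistical Analysis Plan.

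- Replace the three-month phrase with that window.
- Request equipment-provider reports by those dates, whatever the date of visit 3 or of the download, and do the same for subjects who miss visits.
- Count only nights within the window.
- Where only part of the window is available, use the recorded date range to express the outcome as a proportion of observed nights within nights 1 to 84, rather than comparing raw counts from unequal windows. Multiplying the proportion by 84 puts it back in days, and for a complete record this equals the raw count, so all subjects share one scale.

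The change concerns outcome counting only and leaves treatment and visits as they are. It costs a wording change and date-specified requests, and some reports issued for fixed periods may need to be requested again. The proportion also assumes that observed nights represent the unobserved ones, so the number of nights observed should be reported by arm.
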